Since this is a pilot study, the goal is to estimate the magnitude of the effect sizes for use in designing a subsequent study. With 12 patients randomized to each of the two treatment groups, there is only 45% power with an alpha level of 5% to detect a difference of 50% remission rate in the methohexital group and an 80% remission rate in the ketamine group at visit 8. For the other aims, which look at the change in scores on various rating scales over time, there will be 80% power with an alpha level of 5% (2-sided) to detect a difference between the slopes (measuring rate of change in scores on tests per visit) for the two treatment groups of magnitude  $0.05\sigma$ , where  $\sigma$  is the standard deviation of scores in either treatment group at a single visit. If, for example, the standard deviation of the HRSD scores is 5.0, then there will be power to detect an increased rate of improvement in the ketamine group of 0.25 points per visit, corresponding to an average improvement of 2.0 more points per 8 visits in the ketamine group than whatever improvement is observed in the methohexital group (Diggle et al 1995).

Given the recognition that, with the small sample size, power will be low, the primary focus of analysis is to determine whether ECT with ketamine anesthesia compared to ECT with methohexital anesthesia produces a clinically significant effect, i.e., one that, even if it does not reach statistical significance, would justify a larger clinical trial to replicate effect size. We expect a mean number of 8 treatments to remission based on the results of a Consortium for Research in ECT paper.

Our specific hypothesis is that ECT will decrease functional connectivity in the Default Mode Network (time-wise hypothesis). We also think that the decrease in the expression of this network will correlate with the effectiveness of the ECT, or at least will show a difference

between responders and non-responders (group-wise hypothesis). In order to detect network changes, we will calculate seed based correlation, ICA network expressions and amplitude measures of the networks.

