## Seed based correlations

**Nuisance signal regression.** Consistent with common practice in the rs-fMRI literature, nuisance signals will be removed from the data via multiple regressions before functional connectivity analyses will be performed. This step is designed to control for the effects of physiological processes, such as fluctuations related to motion and cardiac and respiratory cycles. Specifically, each individual's 4D time series data will be regressed on nine predictors: white matter (WM), cerebrospinal fluid (CSF), the global signal, and six motion parameters. The global signal regressor will be generated by averaging across the time series of all voxels in the brain. The WM and CSF covariates will be generated by segmenting each individual's high-resolution structural image (using FAST in FSL). The resulting segmented WM and CSF images will be threshold to ensure 80% tissue type probability. These threshold masks will then be

applied to each individual's time series, and a mean time series will be calculated by averaging across time series of all voxels within each mask. The six motion parameters will be calculated in the motion-correction step during preprocessing. Movement in each of the three cardinal directions (X, Y, and Z) and rotational movement around three axes (pitch, yaw, and roll) will be included for each individual. We are aware of the potential problem that the global signal removal might cause by introducing anti-correlating artifacts. Thus we will always compare these calculations to a similar protocol where global signal will not be removed. **Seed selection.** Six 7.5-mm-radius seed regions of interest (ROIs) (containing 33 voxels) centered on the coordinates previously used by Fox et al. will be created to examine functional connectivity for each of six regions, three regions within the "task-positive" network and three within the "default mode" network. The ROIs within the task-positive network will be located in the IPS (-25, -57, 46), the middle temporal region (MT+; -45, -69, -2), and the right frontal eye field (FEF) region of the precentral sulcus (25, -13, 50). The default mode network seed ROIs will be located in the left lateral parietal cortex (LP; -45, -67, 36), medial prefrontal cortex (MPF; -1, 47, -4), and PCC (-5, -49, 40).

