### ICA-Dual regression

The dual-regression approach will be used to identify, within each subject's fMRI data set, subject-specific temporal dynamics and associated spatial maps. This involves (i) using the full set of group-ICA spatial maps in a linear model  $t$  (spatial regression) against the separate fMRI data sets, resulting in matrices describing temporal dynamics for each component and subject, and (ii) using these time-course matrices in a linear model  $t$  (temporal regression) against the associated fMRI data set to estimate subject-specific spatial maps. Finally, the different component maps are collected across subjects into single 4D images (1 per original ICA map, with the fourth dimension being subject identification) and tested voxel-wise for statistically significant differences between groups using nonparametric permutation testing (5,000 permutations). This results in spatial maps characterizing the between-subject/group differences (Figure 3).

[figure not shown]

Figure 3. Dual regression

The biggest advantage of this technique is that it will create functionally and anatomically corresponding spatial maps for every individual, thus making the patterns comparable across subjects. In traditional approaches individual ICA resulted in components where no straightforward comparison was possible.

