### **Amplitude measures**

Amplitude of spontaneous low-frequency fluctuations. To examine the potentially meaningful information contained within the ALFF, two fast-Fourier transformation (FFT)-based indices, ALFF and fALFF, will be used to compute the amplitude of low-frequency fluctuations in the frequency domain. For each individual, ALFF and fALFF will be computed to identify those voxels with significantly detectable low-frequency fluctuation amplitudes. Specifically, at each voxel, ALFF is calculated as the sum of amplitudes within a specific low frequency range (0.01-0.1 Hz). fALFF is the normalized ALFF, calculated by dividing the ALFF value by the total sum of amplitudes across the entire frequency range measured in a given time series. Voxelwise ALFF and fALFF maps will be calculated for each participant in native space, and then will be transformed into the MNI152 standard brain space with 3-mm isotropic voxel size. Before statistical analyses, each individual ALFF or fALFF map will be Z-transformed (i.e., by subtracting the mean voxelwise ALFF or fALFF obtained for the individuals entire brain, and then dividing by the corresponding SD) to improve its suitability for group-level parametric analyses. The individual Z-transformed ALFF or fALFF maps will be used in subsequent group- and center-level analyses. Multiple comparisons will be corrected at the cluster level using Gaussian random field theory (min  $Z>2.3$ ; cluster significance:  $p<0.05$ , corrected).

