### **Group analysis**

Our main goal in our analysis is to determine group-wise effects. The inter-subject variability however poses the main obstacle to gain meaningful effects. We will use our time-wise data to “subtract” measures between time points in the same individual, and analyze our data with repeated measure ANOVA (one factor is time point (intra-subject), other is group (inter-subject)).

Group comparison of the seed based correlation measures is straightforward, correlation values between the vmPFC and other DMN regions and subgenual cingulate will be used to detect any interaction between factors (time and group (responders and non-responders)).

The group analysis of ICA networks will be carried out by dual regression method, as it is presented on Figure 3. Individual network patterns will be obtained, and these individual patterns will be used in a second level analysis with SPM, where voxel based repeated measure ANOVA will be calculated. Similarly individual amplitude maps will be analyzed with SPM.

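### The hypothesis that ECT lowers default mode connectivity has no lead imaging measure, the ICA maps have two tests and no stated familywise correction, and the seed definition contradicts itself

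*Combined protocol and SAP*

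**What the plan says.** Section 13, Data Analysis, gives the imaging claim and its direction: "Our specific hypothesis is that ECT will decrease functional connectivity in the Default Mode Network (time-wise hypothesis". It adds a group-wise claim: the fall will track how well ECT works, "or at least will show a difference" between responders and non-responders. For network changes, "we will calculate seed based correlation, ICA network expressions and amplitude measures of the networks".

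Later sections fill in the measures:

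- **Seed based correlations.** Three DMN seeds and three task-positive seeds are listed, each described as "Six 7.5-mm-radius seed regions of interest (ROIs) (containing 33 voxels". The global signal is one of nine nuisance predictors. Because removing it may create artefactual anti-correlations, the plan adds: "Thus we will always compare these calculations to a similar protocol where global signal will not be removed".
- **ICA-Dual regression.** Component maps are compared between groups voxel by voxel "using nonparametric permutation testing (5,000 permutations".
- **Group analysis.** Seed correlations of the vmPFC with the other DMN regions and with the subgenual cingulate are tested for a time-by-responder interaction. Individual ICA patterns go to a second-level SPM analysis "where voxel based repeated measure ANOVA will be calculated", and the amplitude maps are also analysed in SPM.
- **Amplitude measures.** For ALFF and fALFF only: "Multiple comparisons will be corrected at the cluster level using Gaussian random field theory", with a cluster-forming threshold of Z>2.3 and cluster p<0.05.

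The imaging part of Sample Size and Power recognises that multiple comparisons are inherent, but only as a difficulty for the power calculation. It gives no rule across measures.

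**The concern.** A specific, directional hypothesis needs a result that would count for or against it, fixed before the data are seen. Here several results could fill that role and none is ranked. For the ICA maps even the test is open: two methods are named, neither is said to govern, and neither carries a stated familywise correction. Specifying 5,000 permutations does not by itself say how the voxelwise p-values are adjusted.

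Two things are at stake. One of several unranked results could reach 5% by chance and be reported as support. And since the pilot is meant to supply effect sizes for a larger study, choosing the most favourable measure afterwards would pass on an effect that is too large.

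The seed definition is a separate, smaller matter. Radius and voxel count cannot both be right, so the region that generates the connectivity values is not fixed.

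**Working it through.** **The plan's own figure.** The documents give no familywise error rate and no number of imaging tests. The one imaging figure, 80% power at N=20, is taken from a cited source. It cannot be reproduced because the within- and between-subject variances are not given.

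**Counting the tests.** Taking the listed medial prefrontal seed to be the vmPFC:

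- Seed pairs: vmPFC with two other DMN seeds (left lateral parietal, posterior cingulate) and with the subgenual cingulate, 2 + 1 = 3.
- Global-signal pipelines: 2.
- ICA: 2 named tests, assuming one DMN component.
- Amplitude: ALFF and fALFF, 2.

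Narrow count, connectivity only, one pipeline and one ICA test: 3 + 1 = 4. Broad count: 3 × 2 + 2 + 2 = 10.

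**Chance of at least one significant result when nothing changes.** Each test is taken at two-sided 5%; this is an assumption, because no level is stated for the seed or ICA tests. For k independent tests the chance is 1 − 0.95^k in either direction and 1 − 0.975^k for a decrease. For correlated tests, simulate z_i = √ρ·c + √(1−ρ)·e_i with c and e_i standard normal, and count draws with any |z_i| > 1.96, or any beyond 1.96 in the direction of a decrease (1,000,000 draws). The documents give no correlation, so a range is shown.

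| Correlation | 4 tests, decrease | 10 tests, decrease | 4 tests, either | 10 tests, either |
|---|---|---|---|---|
| 0 | 9.6% | 22.4% | 18.5% | 40.1% |
| 0.3 | 8.7% | 17.8% | 17.4% | 35.1% |
| 0.5 | 7.8% | 14.4% | 15.6% | 28.7% |
| 0.7 | 6.5% | 10.6% | 13.0% | 21.3% |
| 0.9 | 4.7% | 6.4% | 9.3% | 12.8% |
| One lead test | 2.5% | 2.5% | 5% | 5% |

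These figures treat each voxelwise map as a single test held at 5%. That needs a familywise correction within the map, which is stated for the amplitude maps but not for ICA.

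**Seed size.** The section on registration gives 3 mm isotropic voxels, and the individual seed-based analysis extracts seeds in MNI space. Volume check: (4/3)π(7.5)³ / 3³ = 1767.1 / 27 = 65.4 voxels. Counting voxel centres within 7.5 mm gives 81 when the sphere sits on a voxel centre and between 56 and 81 as it is moved off centre. It is never 33. For a 6 mm radius the volume is 904.8 / 27 = 33.5 voxels, and the voxel-centred count is exactly 33.

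**Why a lead measure rather than Bonferroni.** Using a paired t-test with N=20 as a stand-in, 80% power at two-sided 5% needs a standardised change of 0.66. Bonferroni over ten tests (0.05 / 10 = 0.005) raises that to 0.91, and power at 0.66 falls to about 44%.

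**The case against.** The case against is substantial, and most of it bears on size.

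- The vmPFC pairs under Group analysis are tested for a time-by-responder interaction, and the permutation test is between groups. Both serve the group-wise claim, and that section calls group-wise effects its main goal. Counting them all towards the time-wise claim and then doubling for the group-wise one would count them twice. This stands. It also means that the plan does not say which test decides the time-wise claim.
- ALFF and fALFF measure amplitude at each voxel and cannot on their own show a fall in connectivity. The run without global-signal removal reads as a robustness check, and the two ICA tests share the same maps. This stands, and is why the four-test count is given beside the ten.
- The hypothesis is a decrease, so increases should not count as support. This stands; the decrease columns are the main result.
- This is a pilot, imaging is Secondary Aim B, and no passage says that one significant result confirms the hypothesis. This stands too, although Sample Size and Power describes the imaging comparison as the study's main objective, and effect sizes for a later study suffer from unranked selection just as tests do.
- A reader might infer that the subgenual analysis cannot be done because no such seed is listed. It can: each seed is correlated with every voxel in the brain, so only a target region is undefined.

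None of this supplies a lead measure, a choice between the ICA tests or a correction for them.

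**Conclusion.** The gap is real and moderate in size. For a decrease, the chance of at least one false positive is about 7% to 9% with four connectivity tests and 11% to 18% with ten, against 2.5% with one lead test. If either direction is taken as support, it is about 13% to 17% and 21% to 35%, against 5%. These figures assume two-sided 5% per test, correlations of 0.7 to 0.3, and one properly corrected result per map.

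A reader might go further and infer that a false confirmation is likely, or that the plan lets any one of ten results confirm the hypothesis. The documents contain no such rule, and the decrease figures stay well below one half. A reader might also infer that the Z>2.3 cluster rule is itself badly inflated here. The documents give the 6 mm smoothing kernel but not the smoothness of the final maps, so no error rate for that rule can be derived from them.

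The seed inconsistency is certain on the stated 3 mm grid. It is a matter of definition and does not enter the error rates above.

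**What to change.** Before the imaging data are analysed, amend the analysis text as follows.

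1. Name one lead measure for the time-wise hypothesis, for example the mean Fisher-z change over the DMN connections already specified, and say which post-ECT scan is compared with baseline. Declare one global-signal pipeline primary and the other a sensitivity analysis.
2. Name one lead contrast for the group-wise hypothesis.
3. Report ICA, ALFF, fALFF and all other imaging results as exploratory.
4. Use one voxelwise method for the ICA and amplitude maps: permutation with familywise correction, with exchangeability that respects the repeated scans within a person. This replaces the two ICA tests and the Z>2.3 rule.
5. Define the subgenual target region alongside the seeds, and reconcile the seed radius with its voxel count.

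The cost is analysis-plan wording and computer time, with no added patients, scans or visits. The downside is that a striking result on a non-lead measure can be reported only as exploratory.

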## Preprocessing, Overview.

All available resting-state scans were preprocessed using both AFNI (<http://afni.nimh.nih.gov/afni>) and FSL ([www.fmrib.ox.ac.uk](http://www.fmrib.ox.ac.uk)). Specific commands can be found in the preprocessing scripts that are released at [www.nitrc.org/projects/fcon\\_1000](http://www.nitrc.org/projects/fcon_1000). The first four time points of every scan will be discarded, to remove possible T1 stabilization effects, the data will be corrected for motion by aligning each volume to the mean image volume using Fourier interpolation in AFNI. Then the data will be spatially smoothed using a 6-mm FWHM Gaussian kernel. Mean-based intensity normalization will be done by scaling all volumes by the same factor (10,000).

*Seed-based correlation analyses.* The data will be temporally filtered using both a high-pass (Gaussian-weighted least squares straight-line fitting, with  $f = 100.0$  s) and low-pass (Gaussian low-pass temporal filtering, with a HWHM of 2.8 s) filter, followed by linear detrending to remove any residual drift.

*Independent component analysis-Temporal concatenation group analysis.* Consistent with common practice, temporal filtering for ICA analyses will be limited to high-pass filtering (Gaussian-weighted least squares straight-line fitting, with  $f = 100.0$  s).

*Dual regression.* This step will use the same preprocessed data as will be used in the seed-based correlation analyses.

[figure not shown]
*ALFF/fALFF.* No temporal filtering will be carried out, because the data will be examined in the frequency domain within select bands, (fALFF). Temporal despiking with a hyperbolic tangent squashing function will be performed, however, to limit extreme values. Linear trends will then be removed from the data.

*Registration and normalization.* The skull will be removed using AFNI, registration of each individual's high-resolution anatomic image to a common stereotactic space [the Montreal Neurological Institute 152-brain template (MNI152); 3 mm isotropic voxel size] will be done using a 12 degrees of freedom linear affine transformation (FLIRT). The resulting transformation will then be applied to each individual's functional dataset.

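### The plan describes motion and physiological nuisance regression for the functional-connectivity analyses but not for ALFF/fALFF, and no group model has a motion term, so an uneven change in head movement can read as an amplitude change

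*Combined protocol and SAP*

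**What the plan says.** The Preprocessing, Overview section applies common steps to every resting-state scan: the first four volumes are dropped, "the data will be corrected for motion by aligning each volume to the mean image volume using Fourier interpolation in AFNI", and the data are smoothed and intensity-scaled. For ALFF/fALFF it then says "No temporal filtering will be carried out, because the data will be examined in the frequency domain within select bands", adds that "Temporal despiking with a hyperbolic tangent squashing function will be performed, however, to limit extreme values", and ends with "Linear trends will then be removed from the data". The Amplitude measures section sums amplitude over 0.01-0.1 Hz for ALFF, divides by the total amplitude for fALFF, and Z-transforms each map by its own whole-brain mean and SD.

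Nuisance regression appears under Seed based correlations. There, "nuisance signals will be removed from the data via multiple regressions before functional connectivity analyses will be performed", with each series "regressed on nine predictors: white matter (WM), cerebrospinal fluid (CSF), the global signal, and six motion parameters". Its purpose is given as: "This step is designed to control for the effects of physiological processes, such as fluctuations related to motion and cardiac and respiratory cycles".

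The Group analysis section specifies a repeated-measures ANOVA with time point and group as factors. For the amplitude measures it says only "Similarly individual amplitude maps will be analyzed with SPM". From the imaging part of Data Analysis through Sample Size and Power, the text states no motion covariate, motion summary, volume censoring or motion-based exclusion rule.

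**The concern.** Realignment puts the volumes in register but leaves signal changes caused by movement in the series. The seed pipeline reflects this, since it regresses out the six motion parameters after realigning. The amplitude pipeline starts from the same realigned data and names no such step.

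The amplitude comparison is within patient, before and after treatment of a severe depressive episode, and the plan also expects a difference between responders and non-responders. Restlessness or slowing could plausibly change over that interval and could track response. If so, movement would differ between the scans or groups being compared, and a finding attributed to ECT could partly reflect how still the patient lay. Amplitude is one of three kinds of measure that Data Analysis names for detecting network change.

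**Working it through.** The plan states no figure on this point, so there is none to reproduce. The check compares the pipelines and then asks whether the listed amplitude steps would remove a movement difference.

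**1. Scope of the regression**

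| Analysis | Realignment | Motion/WM/CSF regression | Other cleaning named |
|---|---|---|---|
| Seed correlation | yes | yes | high- and low-pass filter, detrending |
| ICA with dual regression | yes | unclear | high-pass filter for the group ICA; dual regression takes the seed-analysis data |
| ALFF/fALFF | yes | not described | despiking, detrending, Z-transform of the map |

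The Aim 2 B paragraph of Data Analysis counts seed correlation and ICA/dual regression as functional connectivity and lists the amplitude measures separately. A step placed before the functional-connectivity analyses therefore does not, on its wording, reach ALFF/fALFF.

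**2. What each amplitude step removes**

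- Despiking limits extreme values, and detrending removes a straight line. Neither removes slow movement-related fluctuation inside 0.01-0.1 Hz.
- The Z-transform removes a uniform effect. If movement multiplies every voxel's amplitude x by a, then (ax - a·mean)/(a·SD) = (x - mean)/SD, so nothing is left. If voxels are inflated unequally, the difference survives.
- Artefact of equal size at both scans cancels from the within-patient difference. Only an unequal change matters.
- fALFF divides by total amplitude. Movement concentrated at low frequencies raises the numerator proportionally more than the denominator, so the ratio still rises.

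**3. Illustration A: simulated pipeline, all inputs assumed**

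The settings were TR 2 s, 150 volumes and 400 voxels, 80 of them motion-sensitive, with no true amplitude change. The steps were tanh despiking, detrending, ALFF/fALFF over 0.01-0.1 Hz and the whole-brain Z-transform, with 300 post-minus-pre differences per setting. The outcome is the mean z over the 80 sensitive voxels. Rejection probability for n = 20 (the figure cited in Sample Size and Power) is approximated as Φ(|mean|/SD × √20 - 1.96). For ALFF at a motion ratio of 1.25 this is Φ(0.182/0.191 × 4.47 - 1.96) = Φ(2.30) = 0.99.

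| Post/pre motion | ALFF shift (z) | Reject | fALFF shift (z) | Reject |
|---|---|---|---|---|
| 1 | -0.01 | 0.04 | -0.02 | 0.05 |
| 1.25 | +0.18 | 0.99 | +0.19 | 0.74 |
| 1.5 | +0.28 | 1.00 | +0.33 | 0.99 |
| 2 | +0.38 | 1.00 | +0.50 | 1.00 |

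With the six motion traces regressed out first, the shifts lie between -0.01 and +0.02 and rejection between 0.03 and 0.08. The simulation regresses the exact traces, so correction of real data would be less complete.

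**4. Illustration B: milder assumptions**

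Suppose movement shifts by 0.5 SD between scans and correlates 0.2 to 0.5 with regional amplitude. The false standardized change is 0.5 × 0.2 = 0.10 to 0.5 × 0.5 = 0.25. With n = 20 and SD of change 1, the noncentrality is 0.10 × √20 = 0.45 to 0.25 × √20 = 1.12. The two-sided 5% t test on 19 df then rejects in 7.1% to 18.6%.

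Both illustrations show the same direction. Their sizes are far apart because they rest on different assumptions.

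**The case against.** The strongest case on the other side has five parts.

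- **The plan does correct for motion.** Every scan is realigned, so the amplitude data are not uncorrected for movement. This stands. What is missing is the second step, which the plan itself takes for connectivity.
- **The regression may reach beyond the seed maps.** A reader might infer that only seed maps are cleaned. The documents do not support that: dual regression is said to use the same preprocessed data as the seed analyses and is classed as functional connectivity. The text is ambiguous there, and the gap shown is confined to amplitude.
- **Treating amplitude differently is not a contradiction.** The plan says what its nuisance step is for and ties it to connectivity; it does not say every measure must have it. It also points to released preprocessing scripts, which could hold further steps and cannot be checked here. Both points stand. The written step list for ALFF/fALFF still omits the regression.
- **There are other safeguards.** Healthy volunteers (10 planned) are scanned three times to address acclimatization and other confounding. They receive no ECT and are not a level of the stated group factor, so they cannot show movement change tied to treatment or response. fALFF normalization and the Z-transform reduce the problem without removing an uneven effect.
- **No error rate follows from the documents.** Artefact forming 5%, 10% or 20% of low-frequency variance raises raw amplitude by 1/√(1 - p) - 1, that is 2.6%, 5.4% or 11.8%, and a reader might take this as the bias. It is not: the analysis uses Z-transformed maps and within-patient differences, where a uniform or constant effect cancels. Nor are the rejection rates above the plan's false-positive rates. They refer to one uncorrected test, whereas the plan applies cluster-level correction to the amplitude maps.

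**Conclusion.** The concern holds in a limited form. As written, ALFF/fALFF has no motion or physiological nuisance regression and the group models have no motion term. A regionally uneven change in head movement between scans, or one associated with response, can therefore be read as an amplitude change. The direction of this conclusion needs only that movement leaves some low-frequency signal after realignment and that it differs between the scans or groups compared. The size cannot be fixed from the documents, which give no motion data.

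A reader might go further and infer that Secondary Aim B as a whole is unprotected. That is not supported: the named hypothesis concerns functional connectivity in the Default Mode Network, and motion regression is planned for the seed analysis that tests it. Amplitude is a supporting measure in a pilot. This is a cheap improvement, not a threat to the trial's main comparison.

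**What to change.** 1. Under ALFF/fALFF in Preprocessing, state that the unfiltered series is regressed on the six motion parameters, already computed at realignment, before ALFF/fALFF is calculated, and give its order relative to despiking. White matter and CSF regressors are optional, because they may alter the low-frequency amplitude being measured; leave the global signal out.
2. Report mean framewise displacement, computed from the same six parameters, by time point and by response group.
3. Repeat the amplitude models of Group analysis with each scan's mean displacement as a covariate, as a sensitivity analysis. Keep it out of the main model: movement may follow clinical response, and adjusting for it could then remove part of a true effect.
4. State explicitly whether nuisance regression also precedes dual regression.

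The cost is script and wording changes only, with no new data. The downside is a few temporal degrees of freedom per scan and possible loss of some real signal that tracks movement.
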